As such, both Philips Respironics and Resmed have participated in the development of the data transfer workflow. Data will flow from the ResMed Airview system or Philips Respironics Encore Anywhere online system, through the necessary API's, managed by Corepoint Health integration engine, into the DatStat study platform. After providing the necessary information to either ResMed Inc. or Philips Respironics's data stewards, which is inclusive of proof of a participant's E-Consent, the participant Name, DOB and CPAP device serial number, the data steward will be required to provide the following data variables via the API workflow:

Weekly Updates on Critical Adherence Monitoring Data Variables

- 1) Total Time Connected (i.e. total time in minutes using a CPAP each evening)
- 2) Air Leakage (i.e. number of minutes the Sleep Apnea Mask is leaking air beyond a given threshold)
- 3) Apnea Hypopnea Index (i.e. a record of the number of apneas an individual is experiencing each evening).

These three variables are critical, quantitative indications, of an individual's adherence to CPAP therapy (i.e. the studies primary outcome) and may also provide insight on how to improve adherence. Monitoring these CPAP therapy variables will help both the research participants and authorized research staff to tailor a participant's goal-setting on a weekly basis, acknowledge progress and troubleshoot difficult weeks. The participants randomized to the proactive care arm will review and discuss their data on a weekly basis with a peer-coach to address these topics. Proactive care participants will also be encouraged to call their Peer-coaches during regular business hours via the C.O.P.D. Information Line and will also be encouraged to chat synchronously or asynchronously with Peer-coaches using the study portal.

Baseline Survey Package

All participants will be assigned a baseline survey package. Together the survey's measure a number of important patient-centered outcomes, like daytime sleepiness, daytime functioning, psychosocial factors influencing the survey's included are:

- 1) Functional Outcomes of Sleep Questionnaire (FOSQ)
- 2) COPD Assessment Test (CAT)
- 3) Epworth Sleepiness Scale (ESS)
- 4) Pittsburgh Sleep Quality Index (PSQI)
- 5) Patient Reported Outcomes Measures Information Systems Survey (PROMIS)

Randomization

A participant must have completed the following steps in order to move on to randomization.

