Participant completes the following steps independently [see Appendix A for randomization workflow]:

- 1) Portal Registration
- 2) E-Consent Signature
- 3) Self-reported confirmation of eligibility survey

Participant and Research Coordinator via First Phone Call:

- 4) Confirmation of Eligibility (i.e. self-report survey and research team confirmation)
- 5) Medical History
- 6) Demographic Information collected by research team
- 7) Self-Report Oxygen Prescriptions and Adherence (if applicable)
- 8) Participants data-steward provides access to CPAP data
- 9) Wireless Data Access confirmed by research team
- 10) ~30-days of baseline CPAP data uploaded to portal (collected retroactively)
- 11) Baseline Survey Package

Once these steps have been completed the research team will be notified both within the study portal and by email; the notification will indicate that the participant is now ready to be randomized.

Envelopes have been made ahead of time and should not be opened ahead of time. The randomization envelope reveals, with equal odds, either the Proactive Care Arm or the Reactive Care Arm. The coordinator will immediately mark the individual as such in their participant profile, within the study portal. See Appendix C for both Respiratory Therapist and Peer Coaching scripts.

Proactive Care Arm

- 1) The Proactive Care arm of the study is considered the study intervention. If an individual is randomized to the proactive care arm they have access to: Weekly Dyadic Peer Coaching
- 2) Respiratory Therapist Dyadic Coaching
- 3) A seven-module online curriculum covering topics on COPD, OSA and Overlap Syndrome
- 4) Web-based access to adherence data
- 5) Proactive, dyadic, web-based and telephone support from Peer Coaches to congratulate progress and troubleshoot difficult weeks

Reactive Care Arm

- 1) Web-based access to adherence data
- 2) Reactive, dyadic, telephone-based support

Figure 1 below shows a simplified, visual representation of the study design.

[figure not shown]

Figure 1.0 Study Design, Study Surveys and Peer Support

Study Activities

Table 1.0 O₂VERLAP Study Activities

Week

Activity	Who's involved?	1	2	3	4	5	6	7	8-15
Portal Registration	Patient	X							
E-Consent	Patient	X							
Self-report eligibility survey	Patient	X							
Confirmation of Eligibility survey	Coordinator	X							
Medical History	Coordinator	X							
Demographic Survey	Coordinator	X							

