Accessing the online curriculum, health monitoring data and peer coaching present minimal risk to study participants. Thus, the project was deemed to not need a data-safety monitoring board.

Overarching approach to analyses

Preliminary analyses will begin by examining the distribution of study variables and provide descriptive statistics (e.g., mean, median, standard deviation, quartiles for continuous variable, frequency and percentage for categorical variables) about the study population. Patient characteristics will be compared among study arms by a series of Kruskal-Wallis tests and Chi-square tests (or Fisher's exact tests as appropriate). Variables on which the groups differ initially will be explored as covariates in subsequent analyses. In case of missing data, appropriate data analytic techniques will be used, which may include deletion, imputation, inclusion of an indicator of missing values, or pattern-mixture modeling. The primary analysis will be as intent-to-treat (including all enrolled subjects) and all analyses will be performed using two- sided tests with alpha=0.05. Analyses will be conducted using SAS and R statistical software. Analysis plans to address each hypothesis are as follows:

Study Primary Aim

Our hypothesis is that CPAP adherence at the 6-week time point will be improved in the proactive care group compared to the reactive care group. Random effects model will be used to compare the mean CPAP adherence over 6 months between proactive and reactive care groups. A random intercept will be included in the model to account for the repeated measures of CPAP

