adherence over 6 months within each patient. Daily CPAP adherence data will be used for the analyses. Multivariable random effects model will be used to assess the difference in CPAP adherence between the proactive care and the reactive care group with adjustment for potential covariates. Adjustments will be made to correct for baseline imbalances across study groups and to adjust for variables known to influence the outcome. Baseline demographic and other clinically important characteristics will be assessed for imbalance among the study groups using Wilcoxon rank sum test, Chi-square or Fisher's exact test, and their association with the outcome using a simple random effects model. These variables will be included as covariates in the multivariable model if found moderately associated with the outcome or unbalanced ($p<0.15$) across groups. All covariates significant at $p<0.10$ will be kept in the final model. As a secondary analysis, we will fit a random effects model to assess the difference in CPAP adherence change between two groups. The random effects model is useful for examining longitudinal measures and it will include all available data. An interaction between time and intervention will be included in the model, both random intercept and random slope will be assessed, likelihood ratio test will be used for model comparison. Similarly, multivariable random effects model will be used to assess this association with adjustment for potential covariates.

Study Secondary Aims

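### The primary aim has two models for one comparison, does not say which decides, and guarantees baseline CPAP use in neither

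*Combined protocol and SAP*

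**What the plan says.** All references are to the combined protocol and SAP.

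- **First model.** Study Primary Aim opens with "Random effects model will be used to compare the mean CPAP adherence over 6 months between proactive and reactive care groups". It has a random intercept for repeated daily values, and no covariates are mentioned.
- **Second model.** The same section then specifies a multivariable random effects model "to assess the difference in CPAP adherence between the proactive care and the reactive care group with adjustment for potential covariates". Its purpose is given as "Adjustments will be made to correct for baseline imbalances across study groups and to adjust for variables known to influence the outcome".
- **Covariate pool and screen.** The pool is generic: "Baseline demographic and other clinically important characteristics will be assessed for imbalance among the study groups". The entry rule is "These variables will be included as covariates in the multivariable model if found moderately associated with the outcome or unbalanced", with p<0.15 printed after the imbalance condition. Covariates with p<0.10 stay in the final model.
- **Change model.** A third model, with a time-by-intervention term, is explicitly labelled: "As a secondary analysis, we will fit a random effects model to assess the difference in CPAP adherence change between two groups".
- **Baseline data.** The Randomization section says "A participant must have completed the following steps in order to move on to randomization", and step 10 of its list is "30-days of baseline CPAP data uploaded to portal (collected retroactively" (approximately 30 days).
- **Contrast.** Study Secondary Aims uses ANCOVA with the baseline score as a fixed covariate.

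The term primary analysis appears once, under Overarching approach to analyses. There it defines the intent-to-treat population, not the model.

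**The concern.** Two statisticians could follow this text faithfully and report different primary p-values. The order of the text favours the unadjusted model, while the directive sentence on adjustment and the reference to a final model favour the adjusted one. Neither is declared.

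The more practical point is precision. A participant's use of the same device over the month before randomization is likely to be the best available predictor of later use. The trial collects it from everyone as a condition of entry, yet the primary aim never commits to using it. The unadjusted model gives up whatever precision it offers. The screened model gives it up if nobody puts baseline use forward as a candidate. The secondary outcomes are better protected than the primary one.

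A lesser, conditional point is that the plan neither states nor excludes claiming success on either model. If that were allowed, type I error would exceed 5%.

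**Working it through.** **Inputs from the documents.** Two-sided alpha is 0.05 (Overarching approach to analyses). The target is 330 recruited for 300 analyzable, with about 10% attrition (Number of subjects), and half go to each arm (Background). That gives 150 per arm.

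**The plan's own figure.** 300 × 1.10 = 330. The stricter 300/0.90 gives 334, and 330 × 0.90 = 297. The target is reproduced to within about 1%. No power, effect size or SD is stated, so there is no power figure to reproduce.

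**Assumptions.** The correlation r between baseline and follow-up participant means is not given; 0.3, 0.5, 0.7 and 0.8 are shown. Effects are in SD units, and 0.25 SD is illustrative.

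**Step 1: formula.** The detectable difference at 80% power is (1.96 + 0.8416) × √(2/150) × √(1 − r²) = 0.3235 × √(1 − r²). Power for 0.25 SD is Φ(0.25 / [√(2/150) × √(1 − r²)] − 1.96).

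| Model | √(1 − r²) | Detectable difference (SD) | Reduction | Power at 0.25 SD |
|---|---|---|---|---|
| Unadjusted | 1 | 0.323 | – | 58% |
| Baseline, r=0.3 | 0.954 | 0.309 | 4.6% | 62% |
| Baseline, r=0.5 | 0.866 | 0.280 | 13% | 71% |
| Baseline, r=0.7 | 0.714 | 0.231 | 29% | 86% |
| Baseline, r=0.8 | 0.600 | 0.194 | 40% | 95% |

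**Step 2: does the plan's screen recover this?** Participant means were simulated with 300 participants, 12 noise covariates and 4,000 runs per setting. Entry was at p<0.15 on association or imbalance and retention at p<0.10. The 0.15 cut-off for association is assumed, because the text attaches it only to imbalance. Results are in order of r:

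- Baseline use forced in, screens kept for the rest: power 61%, 70%, 85%, 94%; type I error 5.3–5.4%.
- Baseline use only a candidate: identical results, and it was retained in all 4,000 runs.
- Baseline use not a candidate: power 57–58% at every r; type I error 5.3–5.6%.

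The Monte Carlo standard error near 5% is √(0.05 × 0.95/4000), or about 0.3 points. The screen alone therefore does little to type I error. What matters is whether baseline use is in the pool.

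**Step 3: nightly data.** A random-intercept analysis was simulated with 10–42 nights per participant, an assumed intraclass correlation of 0.5 and 2,000 runs. Power was 56–57% unadjusted against 60%, 68%, 83% and 93% with baseline use. Type I error was 4.0–6.0% unadjusted and 4.4–5.1% with baseline use.

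**Step 4: if either model could be claimed.** Under the null the two test statistics are bivariate normal with correlation √(1 − r²). The chance that at least one rejects is 6.4%, 7.3%, 8.3% and 8.8%. With the simulated screen and baseline use in the pool it is 6.8%, 7.7%, 8.7% and 9.2%. With baseline use out of the pool and no prognostic candidate it is about 5.7–5.9%.

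**Step 5: how often the choice matters.** In a separate simulation with 10 noise covariates, a true difference of 0.324 SD and baseline use in the pool, the two models disagreed on significance in about 13% of trials at r=0.5 and 17% at r=0.7.

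**The case against.** The best defence is that the text leans towards the adjusted model. Adjustment is stated as something that will be done, the result is called final, and only the change model is labelled secondary. On that reading, prior use of the device is an obvious clinically important characteristic that would be put forward. Step 2 then shows nothing is lost: a candidate baseline covariate is always kept and performs exactly as if forced in. The large gains in Step 1 apply only if the unadjusted model decides or baseline use is left out of the pool. They also rest on an assumed r, and at r=0.3 the gain is under 5%.

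Most of this is fair, and it limits the claim. The size is conditional, the type I point is hypothetical, and the 57–58% power without baseline use assumes that no other candidate is prognostic. It does not remove the gap. No sentence puts baseline use in the pool, and no sentence makes the adjusted model the deciding one. If baseline use would enter anyway, naming it costs nothing. The change model does not help either, since it is labelled secondary and does not say that it uses pre-randomization nights.

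The 6-week hypothesis against a 6-month modelling window, and other Table 1.0 rows marked for the proactive arm only, are separate matters. They need their own correction and do not affect this one.

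**Conclusion.** The concern holds. The deciding model for the primary aim is undeclared, and the most relevant baseline measurement, already required for randomization, is not secured as a covariate. The analysis is not invalid, and either model used alone keeps type I error near 5%.

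The loss if baseline use is left out ranges from small to substantial: a detectable difference 4.6% to 40% larger than necessary when expressed relative to the unadjusted value, for r from 0.3 to 0.8. At r=0.5 the adjustment is worth 1/(1 − 0.25) = 1.33, or about a third more participants. The true value is unknown because r is not in the documents. The loss is nil if the screened model decides and baseline use is a candidate. Type I error of about 6.4–9.2% arises only if success may be claimed on either model with baseline use in the adjusted one. The point should be corrected; confidence is high in the omission and lower in its exact size.

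**What to change.** Before any comparison of outcomes by arm, replace the two competing descriptions in Study Primary Aim with one designated primary model, for example:

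> The primary analysis is a linear random effects model of nightly CPAP use on study arm, with a random intercept for participant and the participant's mean nightly use over the approximately 30 days before randomization as a pre-specified covariate, retained whatever its p-value. The model without covariates is a sensitivity analysis.

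The screens for other covariates can stay; fixing those covariates in advance is good practice but optional. If the screens stay, state the p-value cut-off for association, and say how the baseline mean is formed when fewer than 30 days are available.

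Also reconcile Table 1.0. It marks the baseline CPAP upload as applying to the proactive arm only, whereas the Randomization section requires it before allocation and the Peer Coaches section has all participants review it. Read literally, the table would leave the covariate missing in one arm.

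The cost is SAP wording and one table label, with no new data or procedures.

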Our hypothesis was that the improvement in patient-centered outcomes (daytime functioning and sleep quality) in 6 weeks and 12 weeks will be larger in the proactive care group compared to the reactive group. The change in patient-centered outcomes from baseline to week 6 and week 12 will be compared between the proactive care and the reactive care groups. The difference in change of each outcome will be assessed using analysis of covariance (ANCOVA) with intervention group as a main effect and baseline score as a covariate. Multivariable linear regression analysis will be used to assess the difference in change scores between groups with adjustment for baseline characteristics using similar approaches as described for Hypotheses 1. Baseline variables will be included as covariates in the multivariable linear regression if found moderately associated ($p<0.15$) with the outcome or unbalanced ($p<0.10$) across groups. Only covariates significant at $p<0.10$ will be kept in the final model.

As a secondary analysis, we will also fit a linear random effects model to assess the change from baseline to week 6 by taking into account the correlation of two measurements (baseline and week 6) within each participant as well as using all available data. Long-term maintenance of group effects will be also examined by a linear random effects model to determine whether the change in each outcome (from baseline to 6-week and 12-week follow-up) is different between the study groups.

Study Tertiary Aim

The improvement in the sleep quality and symptoms in 6 weeks and 12 weeks will be larger in the proactive care group compared to the reactive group. The analysis is similar as that listed for the studies secondary aim, please see above.

Potential exploratory analyses

Exploratory analyses are not currently planned, but may be done if warranted.

Addressing heterogeneity of treatment effects (HTE)

To evaluate the HTE, we will assess the interaction between treatment group and several baseline patient characteristics including age, gender, education and socio-economic status. We continue to

think about inclusion of other important sub-groups. If interaction is significant, the treatment effect will be estimated separately for study subgroup.

Data Storage and Confidentiality

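### Covariates for the adjusted models are picked by p-value from the trial's own data, so each model is settled only after outcomes are seen and can leave out variables the plan promises to adjust for

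*Combined protocol and SAP*

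**What the plan says.** Three sections of the combined protocol and SAP describe how covariates are chosen.

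- **Overarching approach to analyses** gives the general rule: "Variables on which the groups differ initially will be explored as covariates in subsequent analyses". All tests are two-sided at the 5% level ("sided tests with alpha=0.05").
- **Study Primary Aim** states the purpose: "Adjustments will be made to correct for baseline imbalances across study groups and to adjust for variables known to influence the outcome". The candidate pool is described but not listed: "Baseline demographic and other clinically important characteristics will be assessed for imbalance among the study groups". Variables enter the multivariable random effects model "if found moderately associated with the outcome or unbalanced ($p<0.15$) across groups". The retention rule is "All covariates significant at $p<0.10$ will be kept in the final model".
- **Study Secondary Aims** says the questionnaires follow an approach like that for adherence. It sets p<0.15 for association with the outcome, enters variables that are associated "or unbalanced ($p<0.10$) across groups", and ends: "Only covariates significant at $p<0.10$ will be kept in the final model". Study Tertiary Aim refers back to this section.

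No covariate is named as one that must stay in the multivariable adherence model. No section mentions an allowance for the selection step. Both aims also have a model that does not use the rule: a random effects comparison of the arms for adherence, and an ANCOVA with baseline score for each questionnaire.

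**The concern.** Three features of the rule work against its stated purpose.

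1. Allocation is random with equal odds (Randomization section). If randomisation is carried out correctly, a significant baseline difference is a chance event. Its p-value does not show whether the variable predicts the outcome, which is what decides whether adjustment helps.
2. The promise is to correct imbalances and to adjust for variables known to influence the outcome. The p<0.10 retention step can undo both. An imbalanced variable unrelated to the outcome usually leaves again, and a known predictor leaves if it misses p<0.10 in this sample.
3. Entry and retention both use the observed outcome, and the pool is not listed. Two analysts following the text could report different adjusted effects. The final model's standard error is then computed as if the covariates had been fixed beforehand.

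At stake are the reproducibility of the adjusted results and, to a lesser degree, their nominal error rate.

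**Working it through.** **Inputs from the documents.** Analysable sample 300 (Number of subjects), allocation 1:1, two-sided alpha 0.05, imbalance cut-off 0.15 (adherence) or 0.10 (questionnaires), association cut-off 0.15 (explicit only for the questionnaires), retention cut-off 0.10. The plan gives no figure for the performance of this rule. Its only sample-size figure is 330 recruited for 300 analysable at about 10% attrition: 300 × 1.10 = 330, while 300/0.90 gives 334 and 330 × 0.90 gives 297. Nothing below depends on that difference.

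**Assumed, because the plan does not say.** The number of candidate variables, their independence, their correlation with the outcome, and one continuous outcome per participant.

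**Step 1: chance imbalance flags.** With K independent candidates and cut-off c, the expected number of flags is Kc and the chance of at least one is 1 − (1 − c)^K.

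| K | c = 0.15: expected, P(≥1) | c = 0.10: expected, P(≥1) |
|---|---|---|
| 10 | 1.5, 80% | 1.0, 65% |
| 20 | 3.0, 96% | 2.0, 88% |

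A variable related to neither arm nor outcome enters with probability 1 − 0.85 × 0.85 = 0.28 under the adherence rule (reading 0.15 for both tests) and 1 − 0.90 × 0.85 = 0.235 under the questionnaire rule.

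**Step 2: what retention removes.** As a rough check, take three predictors with correlations 0.10, 0.15 and 0.20. Residual variance is 1 − (0.01 + 0.0225 + 0.04) = 0.9275, so a predictor's expected z is about r√300/√0.9275. For r = 0.10 this is 1.80, and the chance of missing p<0.10 is about Φ(1.645 − 1.80) = 44%. For r = 0.15 it is Φ(1.645 − 2.70) = 15%, and for r = 0.20 it is Φ(1.645 − 3.60) = 2.5%.

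Simulating the whole rule (4,000 trials per scenario, 10 or 20 candidates, three of them prognostic with r from 0.1 to 0.3) gave slightly higher figures, since a variable must also pass entry. The predictor was left out in 45 to 48% of trials at r = 0.10, about 17% at 0.15 and about 3% at 0.20. Of the variables flagged as imbalanced, 66 to 80% were removed again. With 15 candidates and none prognostic, 90% were removed.

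**Step 3: effect on the treatment test.** Null trials with 300 participants and 8 prognostic candidates (r 0.1 to 0.2), 40,000 per setting, backward elimination at p<0.10 with arm forced in:

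| Candidates | Type I error, selected | Type I error, fixed list | Mean model SE | Empirical SE | Shortfall |
|---|---|---|---|---|---|
| 20 | 5.40% | 4.98% | 0.1040 | 0.1058 | 1.7% |
| 30 | 5.61% | 4.86% | 0.1037 | 0.1065 | 2.6% |

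Monte Carlo error on each rate is √(0.05 × 0.95/40,000) ≈ 0.1 percentage point. About 6 of the 8 real predictors were kept (6.06 and 6.05), with 0.96 and 1.77 unrelated variables. A separate simulation gave 5.3 to 5.5% for the selected model against 4.7 to 4.8% for a fixed list. The Step 2 scenarios gave 5.1 to 5.8% against 4.6 to 5.5%, with Monte Carlo error of about 0.35 points.

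**Step 4: the differing cut-offs.** Both rules were applied to the same simulated trials with 10, 20 and 30 candidates (6,000 each). The final covariate set differed in 1.3%, 3.0% and 4.5% of trials, and the significance verdict on the arm changed in 0.03 to 0.05%.

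**Step 5: power.** With a true effect of 0.324 SD, 15 candidates and correlations 0.3, 0.2 and 0.1, power was 85.0% with the prognostic variables pre-specified, 84.9% with selection and 79.3% unadjusted.

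**The case against.** The strongest reply is that the harm is slight. Type I error moves by less than one percentage point, power is unchanged, and models without any selection exist for both adherence and the questionnaires. That stands, and it limits how much weight the point can carry.

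A second reply is that the Study Primary Aim says covariates meeting p<0.10 will be kept, not that others will be removed. That is fair: dropping is implied there and explicit only in Study Secondary Aims, which does not repeat the promise about known predictors. But a retention threshold that removes nothing would have no function, so the implied reading is the natural one.

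A reader might infer more than the documents support:

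- *That adjusted effects from different covariate sets cannot be compared.* In a linear model under randomisation, the arm coefficient targets the same mean difference whichever baseline covariates are included; precision is what changes. Adherence and questionnaire scores are on different scales in any case.
- *That screening against change scores selects variables through regression to the mean.* The text does not say whether the screen omits the baseline score, and the effect has not been demonstrated.
- *That 0.15 versus 0.10 is itself damaging.* The shared retention step removes most flagged variables, so the two rules almost always end in the same model.
- *That the general section is defective for giving no cut-off.* It is an overview that defers to the aim-specific plans.

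**Conclusion.** The point holds for the multivariable models. Covariates are selected by tests of randomised baselines and of the observed outcome, and the retention step can defeat the adjustment the plan sets out to make. That no allowance is made for selection rests on the plan's silence.

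The main defect is a model that is not fixed in advance. Distortion of the test is secondary: roughly 5.3 to 5.6% type I error instead of 5%, and standard errors 2 to 3% too small, with 300 participants, 20 to 30 independent candidates and 8 weak predictors. The loss of real predictors depends strongly on their assumed strength and is nearly nil at a correlation of 0.20. The daily-data adherence model and correlated covariates could shift all these figures.

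The rule should be changed before data lock, but these figures give no reason to doubt the trial's basic comparison.

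**What to change.** Replace the selection text in Overarching approach to analyses, Study Primary Aim and Study Secondary Aims with a short covariate list, named before data lock and kept whatever the p-values:

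- the outcome's own baseline value: mean CPAP use over the roughly 30 pre-randomisation days for adherence, and the baseline score for each questionnaire;
- a common set chosen on prior clinical grounds from data already collected, such as age, gender, Charlson comorbidities and oxygen prescription.

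Keep the baseline table descriptive, delete imbalance tests as a route into the model, and label any p-value-selected model exploratory.

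One check is needed first. The Randomization section requires the baseline CPAP upload before allocation, but Table 1.0 marks that row as proactive arm only. The two should be reconciled so that the baseline value is clearly available in both arms.

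The cost is SAP wording and prior agreement on the list; no new data are needed. Some listed covariates may prove weak. If each enters as a single term, the example uses 1 + 4 = 5 degrees of freedom against about 300 participants.

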have online access to adherence monitoring data to track their progress as they advance through the study program.

II. Criteria for Subject Selection

Number of subjects

The goal is to recruit 330 participants into the study to result in analyzable data of 300 participants (assumes ~10% attrition).

Gender of Subjects

There are no gender-based enrollment restrictions. Subjects of all genders will be recruited to enroll.

Age of Subjects

Subjects recruited for this study will be adults aged 40 and above.

Racial & Ethnic Origin

There are no enrollment restrictions based on race or ethnicity.

Inclusion Criteria

The inclusion criteria are as follows:

1. Age: ≥ 40 years
2. Primary language: English
3. Diagnosed with both Chronic Obstructive Pulmonary Disease (COPD) and Obstructive Sleep Apnea (OSA)
4. Prescription for positive airway pressure therapy (PAP). There should be no minimum or maximum flow required (i.e., no limitation on PAP modality).
5. Access to the internet via a PC, tablet, or smart phone to complete all study activities from home or remotely
6. PAP device with wireless modem

Exclusion Criteria

1. Non-English speakers
2. Life expectancy less than or equal to six months

Exclusion criteria includes non-English speakers and those whose life expectancy is less than or equal to six months. The study does not currently have the resources to translate the online curriculum into multiple languages, nor does it have the funds to recruit multi-lingual peer coaches. Additionally, as indicated in the inclusion criteria, access to a computer and internet are necessary for participants to complete the study activities.

Vulnerable Subjects

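### Subgroup effects are estimated only after a significant interaction, from an open list, so the differences behind them are overstated on average and moderate ones usually get no subgroup estimate

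*Combined protocol and SAP*

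**What the plan says.** The section Addressing heterogeneity of treatment effects (HTE) is the whole subgroup plan. It reads: "To evaluate the HTE, we will assess the interaction between treatment group and several baseline patient characteristics including age, gender, education and socio-economic status". The authors add that they continue to "think about inclusion of other important sub-groups", and give no date or rule for closing the list. The estimation rule follows: "If interaction is significant, the treatment effect will be estimated separately for study subgroup".

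The significance level comes from Overarching approach to analyses: "all analyses will be performed using two- sided tests with alpha=0.05". No separate level or multiplicity adjustment is given for the interaction tests, so 0.05 is the natural reading of significant.

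The HTE section gives no categories or cut-points and names no outcome or time point. The primary hypothesis is that "CPAP adherence at the 6-week time point will be improved in the proactive care group", but nothing ties HTE to it. The section on potential exploratory analyses leaves room for unplanned ones. Number of subjects plans 330 recruited to yield 300 analyzable. No power, target effect or SD appears anywhere.

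**The concern.** The rule makes a significance test decide whether subgroup effects are estimated at all. This has two consequences.

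- **Selection.** An interaction reaches significance only if its estimate is large relative to its standard error. The differences that lead to subgroup effects being shown are therefore a selected set, larger on average than the truth.
- **Silence.** In a trial sized without reference to interactions, a moderate true difference will usually miss the threshold and get no subgroup estimates. A non-significant p-value without an interval cannot separate no difference from too little data.

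The open list adds to both, because a reader will not know how many factors were tried unless the report says so. At stake is the interpretation of who benefits from proactive coaching. The primary comparison is not affected.

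**Working it through.** **Inputs from the documents.** 300 analyzable; equal allocation (Randomization: "The randomization envelope reveals, with equal odds, either the Proactive Care Arm or the Reactive Care Arm"), taken as 150 per arm; two-sided alpha 0.05; four named factors.

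**Assumptions, because the documents are silent.** One value per participant with common SD; an overall effect with 80% power (90% as a check); two-category subgroups split 50/50, 30/70 or 20/80.

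**The plan's own figure.** 300 × 1.10 = 330, and 330 × 0.90 = 297. Dividing instead, 300/0.90 gives 334. The stated 330 for about 300 reproduces closely enough.

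**Step 1: overall effect.** SE = √(4/300) = 0.1155 SD. The effect with 80% power is 2.80 × 0.1155 = 0.323 SD. With 90% power it is 0.374 SD.

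**Step 2: interaction SE.** For subgroup share s, SE = √(4/300) × √(1/s + 1/(1−s)).

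- 50/50: 0.1155 × 2.00 = 0.231 SD
- 30/70: 0.1155 × 2.18 = 0.252 SD
- 20/80: 0.1155 × 2.50 = 0.289 SD

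The smallest estimate that can be significant is 1.96 × SE: 0.45, 0.49 and 0.57 SD. These are also the true differences at which power reaches 50%.

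**Step 3: power and overstatement.** Let δ be the true interaction divided by its SE. Power = Φ(δ − 1.96) + Φ(−δ − 1.96). Average overstatement = E(|Z| given |Z| > 1.96)/δ, with Z normal, mean δ and variance 1.

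Worked case (interaction equal to the overall effect, 50/50): δ = 0.3235/0.2309 = 1.401. Power = Φ(−0.559) + Φ(−3.361) = 0.2881 + 0.0004 = 0.2885. The conditional mean of |Z| is (1.401 × 0.2877 + 0.3426)/0.2885 = 2.585, and 2.585/1.401 = 1.845. Here 0.2877 is the difference of the two Φ terms and 0.3426 is the sum of the normal densities at 0.559 and 3.361.

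Power and average overstatement, overall effect at 80% power:

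| True interaction ÷ overall effect | 50/50 | 30/70 | 20/80 |
|---|---|---|---|
| 0.5 | 10.8%, 3.5× | 9.8%, 3.8× | 8.7%, 4.3× |
| 1 | 28.8%, 1.8× | 25.0%, 2.0× | 20.2%, 2.2× |
| 1.5 | 55.6%, 1.3× | 48.6%, 1.4× | 39.0%, 1.6× |
| 2 | 80.0%, 1.1× | 72.8%, 1.2× | 61.1%, 1.3× |

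With the overall effect at 90% power, an interaction of equal size has 36.7%, 31.8% and 25.4% power and is overstated 1.6, 1.8 and 2.0 times.

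**Step 4: what happens to the two subgroup effects.** These are simulated means given significance, 50/50 split, overall effect 0.323 SD.

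- Interaction equal to the overall effect: true 0.485 and 0.162 SD; reported on average 0.62 and 0.03 SD.
- No interaction: true 0.323 SD in both; on average the larger reported effect is 0.59 SD and the smaller 0.05 SD.

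**Step 5: false findings with no true interaction.** Independent tests, one outcome: 1 − 0.95⁴ = 18.5% for the four named factors. If additions took the list to six, 1 − 0.95⁶ = 26.5%.

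**The case against.** Requiring a formal interaction test before looking at subgroups is a recognised guard against over-reading separate subgroup results. The plan uses baseline characteristics only, names four, and keeps HTE apart from its aims. That is fair, and the test can stay. What does not follow is that estimation should depend on its result.

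Three stronger readings are tempting, and the documents do not support them.

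- **Every reported subgroup effect is exaggerated.** It is the difference that is overstated on average; of the two effects, one moves up and the other down. For large interactions the bias is small. At twice the overall effect, 37.5% (50/50) and 31.3% (30/70) of the significant simulated differences did not exceed the truth.
- **Real differences mostly go unreported.** That depends on size. It fits differences below about 0.45-0.57 SD, depending on the split, and not larger ones.
- **Non-significant interactions will be withheld.** The section says without condition that interactions will be assessed. Only the separate subgroup effects are conditional. The plan is silent on how non-significant results, or the number of tests, will be reported.

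The numerical caveats also stand. Power and overstatement come from assumed scenarios and vary widely across them. Age might be modelled continuously, in which case the two-category model would not apply to it. Education and socio-economic status are plausibly correlated, which would lower the 18.5%.

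**Conclusion.** The point holds as a cheap improvement to a supporting analysis. The selection follows from the written rule and needs no assumption about effect size; its magnitude does.

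Under the stated assumptions, power for an interaction half to twice the overall effect runs from about 9% to 80%, and average overstatement from 4.3-fold down to 1.1-fold. In the middle case, an interaction equal to the overall effect, the difference gets no subgroup estimates 71-80% of the time. The ratios in the table depend only on the assumed overall power, the split and the relative size of the interaction. The SD figures also use the 300 analyzable participants. The 18.5% uses only alpha, four factors and independence. Because no HTE outcome is named, the number of tests could be larger than four.

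**What to change.** In the HTE section:

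1. Remove the significance condition on estimating subgroup effects.
2. Before outcome data are examined, close the list of characteristics and set the categories for each (or state that age is modelled continuously). Name the HTE outcome and time point.
3. Report every listed interaction estimate and every subgroup effect with a 95% CI whatever the p-value. Label them exploratory and state how many interactions were tested.

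The interaction test can remain as the guard against over-reading. This removes the bias from selecting on significance, but it does not add precision: the interaction CI half-width is 1.96 × 0.231 = 0.45 SD at 50/50 and 1.96 × 0.289 = 0.57 SD at 20/80. Readers would see that uncertainty.

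The cost is a few sentences in the plan and one more table or forest plot with wide intervals. The primary analysis is unchanged.
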